## STUDY PROTOCOL

### Study information

Title	Safety Profile of BNT162b2 mRNA SARS-CoV-2 Vaccine in Indonesia: A National Passive Surveillance.
Protocol number	C4591050
Protocol version identifier	Version 2.0
Date	26 April 2023
Active substance	ATC code: J07BX03 Tozinameran - Nucleoside-modified messenger RNA (modRNA) encoding the viral spike glycoprotein (S) of SARS-CoV-2
Medicinal product	BNT162b2 mRNA Vaccine
Research question and objectives	
The objective of the study is to characterize descriptively the BNT162b2 vaccination experience among the Indonesian population, by analyzing structured data within Indonesia Vaccine Safety Database as requested by Indonesia Food and Drug Monitoring Agency (BPOM).
 
Specific data elements include:
 

A. Primary outcome measure :

A1. SAE (Serious Adverse Event) : SAE after primary dose and/or booster dose

A2. Total AE reported after primary dose and/or booster dose

B. Secondary outcome measure :

B1. SAE onset : <math>\leq</math>30 mins or <math>></math> 30 mins

PFIZER CONFIDENTIAL

A large rectangular area of the page is completely blacked out with a thick black marker, obscuring several lines of text.

	
B2. Causality of SAE : coincidence, ISRR (Immunization Stress Related Response), vaccine reaction, unclassifiable, or indeterminate
 
B3. Type of AE :
 
B3.1. Serious and Non-serious
 
B3.2. Solicited and unsolicited
 
B4. Solicited AEs:
 
B4.1.. Local reactions : pain, swelling, redness, thickness.
 
B4.2. Systemic reactions: fever, myalgia, malaise
 
B5. Unsolicited AEs:
 
B5.1. Local reactions: abscess, bleeding, etc.
 
B5.2. Systemic reactions: headache, nausea, arthralgia, etc.

Author	
PPD MD
 
Pfizer
 
PPD

[figure not shown]
This document contains confidential information belonging to Pfizer. Except as otherwise agreed to in writing, by accepting or reviewing this document, you agree to hold this information in confidence and not copy or disclose it to others (except where required by applicable law) or use it for unauthorized purposes. In the event of any actual or suspected breach of this obligation, Pfizer must be promptly notified.

PFIZER CONFIDENTIAL

## 2. LIST OF ABBREVIATIONS

Abbreviation	Definition
AE	Adverse event
BPOM	Indonesia Food and Drug Monitoring Agency
CIOMS	Council for International Organizations of Medical Sciences
COVID-19	Coronavirus Disease 19
EU	European Union
EUA	Emergency Use Authorization
FDA	Food and Drug Administration
GPP	Good Pharmacoepidemiology Practices
IBM-SPSS	Intelligence Based Manufacturing – Statistical Package of Social Science
IRB	Institutional Review Board
ISRR	Immunization Stress Related Response
IQR	Interquartiles Ranges
modRNA	Modified Ribonucleocid Acid
MoH	Ministry of Health
mRNA	Messenger Ribonucleic Acid
NCAEFI	National Committee of Adverse Event Following Immunization
NI	Non Interventional
SAE	Serious Adverse Events

PFIZER CONFIDENTIAL

SAP	Statistical Analysis Plan
SARS-CoV-2	Severe Acute Respiratory Syndrome Coronavirus 2
WHO	World Health Organization

PFIZER CONFIDENTIAL

[figure not shown]

#### 4. ABSTRACT

None

#### 5. AMENDMENTS AND UPDATES

Amendment number	Date	Protocol section(s) changed	Summary of amendment(s)	Reason
1 administrative	26 Apr 2023	Section 6 MILESTONE S	Modified Milestone	NA
		Section 9 RESEARCH METHODS	Deletion of text of SAP: Detailed methodology for summary and statistical analyses of data collected in this study will be documented in a statistical analysis plan (SAP),etc	Align with study team's decision.

PFIZER CONFIDENTIAL

## 6. MILESTONES

Milestone	Planned date
Start of data collection	16 March 2023
End of data collection	28 March 2023
Final study report	19 June 2023

## 7. RATIONALE AND BACKGROUND

BPOM (Indonesia National Regulatory Authority) has issued an Emergency Use Authorization (EUA) to permit the emergency use of Comirnaty 30 mg/dose for primary and 15 mg/dose for booster concentrate for dispersion for injection. Comirnaty is indicated for active immunization to prevent COVID-19 caused by SARS-CoV-2 virus, in individuals 12 years of age and older in Indonesia. For detailed information please refer to the BPOM (Indonesia National Regulatory Authority) approved Fact Sheet For Health Care Providers EUA Of Comirnaty.

The safety of the primary series Pfizer-BioNTech COVID-19 Vaccine was evaluated in participants 6 months of age and older in 3 clinical studies conducted in the United States(US), Europe, Turkey, South Africa, and South America. Study BNT162-01 (Study 1) was a Phase 1/2, second-part, dose-escalation trial that enrolled 60 participants, 18 through 55 years of age. Study C4591001 (Study 2) is a Phase 1/2/3, multicenter, multinational, randomized, saline placebo-controlled, observer-blind, dosefinding, vaccine candidate-selection (Phase 1) and efficacy (Phase 2/3) study that has enrolled approximately 46,000 participants, 12 years of age or older. Of these, approximately 43,448 participants [21,720 Pfizer-BioNTech COVID-19 Vaccine (30 mcg modRNA); 21,728 placebo] in Phase 2/3 are 16 years of age or older (including 138 and 145 participants 16 and 17 years of age in the vaccine and placebo groups, respectively) and 2,260 participants are 12 through 15 years of age (1,131 and 1,129 in the vaccine and placebo groups, respectively). Study C4591007 (Study 3) is a Phase 1/2/3 multicenter, randomized, dose-finding, open-label (Phase 1) and multinational, saline placebo-controlled, observer-blind, immunogenicity and efficacy (Phase 2/3) study that has enrolled 4,695 participants 5 through 11 years of age, of whom 3,109 participants received Pfizer-BioNTech COVID-19 Vaccine (10 mcg modRNA) and 1,538 participants received placebo in Phase 2/3. Study

PFIZER CONFIDENTIAL

3 also enrolled 1,776 participants 6 through 23 months of age, of whom 1,178 participants were in the Pfizer-BioNTech COVID-19 Vaccine (3 mcg modRNA) group and 598 participants in the placebo group; and also enrolled 2,750 participants 2 through 4 years of age, of whom 1,835 participants were in the Pfizer-BioNTech COVID-19 Vaccine group and 915 participants in the placebo group in Phase 2/3. Results from these clinical studies have been published in peer-reviewed journals.

BPOM (Indonesia National Regulatory Authority) has requested to conduct an analysis of AEs reported in the Indonesia NC AEFI database following administration of BNT162b2 mRNA vaccine.

## **8. RESEARCH QUESTION AND OBJECTIVES**

The objective of the study is to characterize descriptively the BNT162b2 vaccination safety experience among the Indonesian population, by analyzing structured data within Indonesia Vaccine Safety Website (Ministry of Health) as requested by BPOM (Indonesia National Regulatory Authority).

## **9. RESEARCH METHODS**

### **9.1. Study design**

This is a descriptive study for secondary data collection and analysis of structured data regarding AEs reported in Indonesia Vaccine Safety Website, following administration of primary and booster dose BNT162b2 mRNA vaccine. This study will not provide or make recommendations on any vaccine use.

A. The AEs reported in Indonesia Vaccine Safety Database, following administration of BNT162b2 mRNA vaccine, are expected to be structured and anonymized/ coded. Individual vaccine recipient identification information will not be collected in this study. The following data elements will be collected from the Indonesia Vaccine Safety Website for further analysis. Primary outcome measure :

A1. SAE (Serious Adverse Event) : SAE after primary dose and/or booster dose

A2. Total AE reported after primary dose and/or booster dose

B. Secondary outcome measure :

B1. SAE onset :  $\leq$ 30 mins or  $>$  30 mins

B2. Causality of SAE : coincidence, ISRR (Immunization Stress Related Response), vaccine reaction, unclassifiable, or indeterminate

PFIZER CONFIDENTIAL

**B3. Type of AE :**

B3.1. Serious and Non-serious

B3.2. Solicited and unsolicited

**B4. Solicited AEs:**

B4.1.. Local reactions : pain, swelling, redness, thickness.

B4.2. Systemic reactions: fever, myalgia, malaise

**B5. Unsolicited AEs:**

B5.1. Local reactions: abscess, bleeding, etc.

B5.2. Systemic reactions: headache, nausea, arthralgia, etc.

Since the study doesn't involve primary data collection from any participants, there will be no requirement of individual consent/ assent.

**9.2. Setting**

The secondary data collection will be exclusively from the Indonesia Vaccine Safety Website as requested by BPOM (Indonesia National Regulatory Authority). After the study protocol is approved by BPOM (Indonesia National Regulatory Authority), structured data will be obtained retrospectively for all AEs reported following administration of the BNT162b2 mRNA vaccine, starting from the time of vaccine available in Indonesia. Structured anonymized data for events which includes the following information will be collected and used for analysis:

**A. Primary outcome measure :**

A1. SAE (Serious Adverse Event) : SAE after primary dose and/or booster dose

A2. Total AE reported after primary dose and/or booster dose

**B. Secondary outcome measure :**

B1. SAE onset :  $\leq$ 30 mins or  $>$  30 mins

B2. Causality of SAE : coincidence, ISRR (Immunization Stress Related Response), vaccine reaction, unclassifiable, or indeterminate

**B3. Type of AE :**

B3.1. Serious and Non-serious

B3.2. Solicited and unsolicited

**B4. Solicited AEs:**

PFIZER CONFIDENTIAL

B4.1.. Local reactions : pain, swelling, redness, thickness.

B4.2. Systemic reactions: fever, myalgia, malaise

B5. Unsolicited AEs:

B5.1. Local reactions: abscess, bleeding, etc.

B5.2. Systemic reactions: headache, nausea, arthralgia, etc.

Events for which either of the above is missing will not be recorded for analysis.

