### **9.2.2. Exclusion criteria**

The incomplete data in the database will be excluded

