### **9.3. Variables**

Variable	Role	Data source(s)	Operational definition
The type of vaccination with BNT162b2 mRNA vaccine following which SAE was reported	Baseline characteristics	Indonesia Vaccine Safety Website	Whether the AE was reported after primary series or booster vaccination
Onset of SAE	Baseline characteristic	Indonesia Vaccine Safety Website	Whether the serious AE onset $\leq$ 30 mins or $>$ 30 mins
Causality	Baseline characteristics	Indonesia Vaccine Safety Website	Whether the SAE was caused by the vaccine. Causality of the AE with BNT162b2 – classified as WHO criteria as coincidence, ISRR, vaccine reaction, unclassifiable, or indeterminate)
Type of AE	Baseline characteristics	Indonesia Vaccine Safety Website	Whether the AE was Serious and Non-serious or solicited and unsolicited

PFIZER CONFIDENTIAL

Type of solicited reaction	Baseline characteristics	Indonesia Vaccine Safety Website	Whether the AE was local or systemic
Type of Solicited Local reaction	Baseline characteristics	Indonesia Vaccine Safety Website	Whether the AE was pain, swelling, redness or thickness
Type of Solicited Systemic reaction	Baseline characteristics	Indonesia Vaccine Safety Website	Whether the AE was fever, myalgia, malaise
Type of unsolicited reaction	Baseline characteristics	Indonesia Vaccine Safety Website	Whether the AE was local or systemic and the term reported
Type of unsolicited local reaction	Baseline characteristics	Indonesia Vaccine Safety Website	Whether the AE was abscess, bleeding, etc.
Type of unsolicited systemic reaction	Baseline characteristics	Indonesia Vaccine Safety Website	Whether the AE was headache, nausea, athralgia, fatigue, etc
Seriousness	Baseline characteristics	Indonesia Vaccine Safety Website	Whether the AE was serious according to Indonesia MoH decree (require hospitalization, life-threatening, cause persistent or significant disability/ incapacity, or suspected to cause death) or non-serious

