#### 9.5. Study size

This is a descriptive study without a statistical hypothesis and hence sample size calculation is not applicable. In this study all the AEs reported following administration of BNT162b2 mRNA vaccine

will be collected retrospectively from the onset of this vaccine administration in Indonesia till the time of approval of this study.

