#### **9.7. Data analysis**

Descriptive Summary statistics will be presented to describe characteristics of events reports. Categorical covariates such as gender will be described by frequency distributions while continuous covariates such as age expressed will be summarized by in terms of their means and standard deviations or medians and interquartile ranges (IQR) as appropriate.

In addition, incidence rates will be computed as the number of events divided by the total number of vaccines administered.

All analyses will be done by Microsoft Excel

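### The completeness rule does not say which blank fields exclude an event; any event it excludes leaves the numerator but not the denominator, so the SAE and AE rates can only stay the same or fall

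*Combined protocol and SAP*

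**What the plan says.** Section 9.2 introduces its list of outcomes with "Structured anonymized data for events which includes the following information will be collected and used for analysis". The list runs from the primary outcomes (A1, SAEs; A2, all AEs) through SAE onset (B1), SAE causality (B2) and AE type (B3) to solicited and unsolicited reactions (B4, B5). Directly after B5 comes the completeness rule: "Events for which either of the above is missing will not be recorded for analysis".

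Section 9.2.2 gives one exclusion criterion: "The incomplete data in the database will be excluded". It does not say what makes data incomplete, or whether a blank field or the whole record is excluded.

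The second primary outcome reads "A2. Total AE reported after primary dose and/or booster dose". Section 9.7 states that "incidence rates will be computed as the number of events divided by the total number of vaccines administered". It gives no missing-data category, count of excluded events or sensitivity analysis.

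Section 9.3 defines onset by "Whether the serious AE onset" fell within 30 minutes or later, with no category for unknown. Causality has five categories, two of which (unclassifiable and indeterminate) cover assessments that reached no clear answer.

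**The concern.** The rule acts on events, not on table cells. An event removed because one descriptive field is blank is lost from the totals as well as from the table for that field. If onset and causality are among the fields that count, a secondary descriptor decides whether an SAE enters the first primary outcome.

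The denominator is not reduced to match, so the effect on a rate has one direction only. This is a safety description requested by the regulator, and an SAE rate that can be lowered but never raised by incomplete reporting needs at least a stated count of what was left out. Proportions among events, such as the serious share or the causality mix, could move either way.

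The rule also sits badly with A2, which is worded as a total of what was reported.

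**Working it through.** **1. What the rule can cover.** Three readings of the back-reference in section 9.2:

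| Reading | Consequence |
|---|---|
| Every listed item, literally | Drops every non-serious AE, since these have no SAE onset or causality. This cannot be meant. |
| Listed items that apply to the event | Drops an SAE with blank onset or no causality entry from A1 and A2. Fits the lead-in sentence, but the word *applicable* is not in the text. |
| Only the reaction items just above (B4 and B5) | Drops no SAE for blank onset or causality. Section 9.2.2 still could. |

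The protocol does not choose. On the second reading, an SAE coded unclassifiable or indeterminate has an entry and stays; only one with no causality entry is at risk. For non-serious AEs the fields at risk are dose type, seriousness, solicited or unsolicited class, and reaction type.

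**2. Direction.** Let S be the eligible reported SAEs, k ≥ 0 the number excluded, and D the vaccines administered (taken as doses). Without the rule the rate is S/D. With it, the rate is (S − k)/D ≤ S/D, with equality only when k = 0. The same holds for all AEs. This needs no assumed figures.

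**3. Size, second reading, illustration only.** The plan states no rate, event count or missingness, so there is no figure to reproduce. Let a and b be the assumed shares of SAEs with blank onset and blank causality. Whatever the dependence between them, the share of SAEs kept lies between 1 − a − b and 1 − max(a, b).

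| a | b | SAEs kept | All-eligible rate ÷ reported rate |
|---|---|---|---|
| 0% | 0% | 100% | 1.00 |
| 5% | 0% | 95% | 1/0.95 = 1.05 |
| 5% | 2% | 93% to 95% | 1.05 to 1.08 |
| 5% | 5% | 90% to 95% | 1.05 to 1.11 |
| 10% | 10% | 80% to 90% | 1.11 to 1.25 |

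With an assumed 20 SAEs at 5% and 5%, the loss is 20 × 0.05 = 1 to 20 × 0.10 = 2 events. On the third reading, section 9.2 loses 0 SAEs for these blanks.

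**4. Effect on A2 and on the serious share.** Assume 5% of AEs are serious.

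- 90% of SAEs kept, no other loss: AEs kept = 0.05 × 0.90 + 0.95 = 0.995. The serious share reads 0.045/0.995 = 4.5%.
- Dose type blank in 5% of non-serious AEs and in no SAE: AEs kept = 0.05 + 0.95 × 0.95 = 0.9525. The serious share reads 0.05/0.9525 = 5.2%.

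So A2 barely moves if only SAE fields are blank, and the serious share can go down or up.

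**The case against.** **The SAE-dropping reading is not the only one.** It needs a qualifier that the text does not contain. *Either* suggests a pair, and the sentence directly follows B4 and B5. This stands. A reader might infer that the plan does remove SAEs with blank onset or causality from A1. The documents support only that it may.

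**There is no strict conflict with the collection statements.** A reader might set the rule against section 9.2, where "structured data will be obtained retrospectively for all AEs reported following administration of the BNT162b2 mRNA vaccine", and against section 9.5, whose sentence beginning "In this study all the AEs reported following administration of BNT162b2 mRNA vaccine" goes on to say that they will be collected. Both concern what is obtained; the completeness rule concerns what is analysed. Wide collection followed by narrower analysis is ordinary, and the age limit in section 9.2.1 narrows in the same way. This stands. Only the wording of A2 as a total remains in tension.

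**Nothing shows that any event is affected.** The data are described as structured, and the two onset categories do not show how the database records an unknown onset. This stands on size, not on direction.

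**The report may still disclose exclusions.** Silence in the protocol does not stop the study report from giving counts, and the data management plan promised in section 9.6, which is not among the documents, may define completeness. This is fair, but a rule that decides what enters a primary count belongs in the protocol.

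**The study is descriptive, on unvalidated passive reports, so a definition and exclusion counts might be enough.** In part. They would make the loss visible but leave it in the primary rates, and keeping the events costs little more.

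**Conclusion.** The concern holds in limited form. The plan states an event-level exclusion, leaves its scope undefined, and pairs it with a denominator that does not change. Any exclusion therefore leaves the SAE and AE rates the same or lower, relative to all eligible reported events. On a plausible reading, SAEs with blank onset or no causality entry are among those lost from A1 and A2. On the narrower reading of section 9.2 they are not, unless section 9.2.2 removes them.

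The size is unknown and may be zero. The blank rates, the 20 SAEs and the 5% serious share used above are all assumptions. A reader might also infer that true incidence is understated by these amounts. The documents do not support that, because the comparison is with reported events under passive surveillance and says nothing about events never reported.

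The direction is certain, the scope is ambiguous and the remedy is cheap, so this should be fixed before the final report.

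**What to change.** Replace the completeness sentence in section 9.2 and the criterion in section 9.2.2 with:

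> Every eligible reported AE (age recorded as 12 years or older) is counted in A2, and every such AE recorded as serious is counted in A1. A blank onset or causality (SAEs only), dose type, seriousness, solicited/unsolicited class or reaction type is tabulated as Unknown and does not remove the event. Events with blank seriousness count in A2 and are reported separately, as they cannot be assigned to A1, so A1 is a minimum count. Events with missing age are reported separately.

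Report the number missing per field. Add one sensitivity table of counts and rates restricted to complete records, defined as records with every section 9.3 field that applies to that event filled.

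Data collection was planned to end on 28 March 2023, before this version's date of 26 April 2023. If incomplete records were not extracted and cannot be obtained, report any exclusion counts the data owner can supply and state that the rates are lower bounds relative to all eligible reports.

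The cost is one paragraph, an Unknown row per table, one extra table and possibly one further data request, which depends on the data owner. Reported rates may be slightly higher. The main counts will include less complete records, and section 9.9 rules out validation; the sensitivity table keeps the completeness screen visible.

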### **9.2.1. Inclusion criteria**

This study will include adverse events reported in Indonesia NC AEFI database for individuals 12 years of age and older

### **9.2.2. Exclusion criteria**

The incomplete data in the database will be excluded

### **9.3. Variables**

Variable	Role	Data source(s)	Operational definition
The type of vaccination with BNT162b2 mRNA vaccine following which SAE was reported	Baseline characteristics	Indonesia Vaccine Safety Website	Whether the AE was reported after primary series or booster vaccination
Onset of SAE	Baseline characteristic	Indonesia Vaccine Safety Website	Whether the serious AE onset $\leq$ 30 mins or $>$ 30 mins
Causality	Baseline characteristics	Indonesia Vaccine Safety Website	Whether the SAE was caused by the vaccine. Causality of the AE with BNT162b2 – classified as WHO criteria as coincidence, ISRR, vaccine reaction, unclassifiable, or indeterminate)
Type of AE	Baseline characteristics	Indonesia Vaccine Safety Website	Whether the AE was Serious and Non-serious or solicited and unsolicited

PFIZER CONFIDENTIAL

Type of solicited reaction	Baseline characteristics	Indonesia Vaccine Safety Website	Whether the AE was local or systemic
Type of Solicited Local reaction	Baseline characteristics	Indonesia Vaccine Safety Website	Whether the AE was pain, swelling, redness or thickness
Type of Solicited Systemic reaction	Baseline characteristics	Indonesia Vaccine Safety Website	Whether the AE was fever, myalgia, malaise
Type of unsolicited reaction	Baseline characteristics	Indonesia Vaccine Safety Website	Whether the AE was local or systemic and the term reported
Type of unsolicited local reaction	Baseline characteristics	Indonesia Vaccine Safety Website	Whether the AE was abscess, bleeding, etc.
Type of unsolicited systemic reaction	Baseline characteristics	Indonesia Vaccine Safety Website	Whether the AE was headache, nausea, athralgia, fatigue, etc
Seriousness	Baseline characteristics	Indonesia Vaccine Safety Website	Whether the AE was serious according to Indonesia MoH decree (require hospitalization, life-threatening, cause persistent or significant disability/ incapacity, or suspected to cause death) or non-serious

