#### **9.6. Data management**

Data will be obtained from the Indonesia Vaccine Safety Website for AEs reported following administration of BNT162b2 mRNA vaccine as per the variables listed in section 9.3. A data management plan will be created before data collection begins and will describe all functions, processes, and specifications for data collection and analysis.

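### The missing-item rule can remove SAEs from the primary counts, and the per-vaccine 'incidence rate' is really a reporting ratio

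*Combined protocol and SAP*

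**What the plan says.** **Missing items.** Section 9.2 (Setting) lists the primary outcomes (A1 SAEs, A2 all AEs) and the secondary ones (B1 SAE onset, B2 SAE causality, B3 type, B4 solicited terms, B5 unsolicited terms). It closes with "Events for which either of the above is missing will not be recorded for analysis". Section 9.2.2 adds that incomplete data are excluded and does not say what counts as incomplete. Section 9.3 gives onset two classes: "Whether the serious AE onset $\leq$ 30 mins or $>$ 30 mins".

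**Scope.** Section 9.2 also says that "structured data will be obtained retrospectively for all AEs reported following administration of the BNT162b2 mRNA vaccine", and section 9.5 says that the AEs "will be collected retrospectively from the onset of this vaccine administration in Indonesia till the time of approval of this study". The inclusion criterion in section 9.2.1 limits events by age only: "This study will include adverse events reported in Indonesia NC AEFI database for individuals 12 years of age and older". No section sets a maximum interval from dose to onset.

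**Rate.** In section 9.7, "incidence rates will be computed as the number of events divided by the total number of vaccines administered". The study title calls the design "A National Passive Surveillance". The limitations in section 9.9 cover dependence on the data owner and the absence of validation. They mention neither passive reporting nor the period after a dose in which an event can be counted.

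**The concern.** The SAE count is a primary result of this descriptive study. Under the rules as written, whether an SAE counts in A1 can depend on whether a secondary field was filled in. Onset and causality are listed for SAEs only, so missing values in those two fields can remove serious events but not non-serious ones. That would lower the SAE count and the serious share in B3.1. The rule also sits uneasily with the statements in sections 9.2 and 9.5 that all reported AEs are obtained, so a reader cannot tell whether A1 counts all reports or only complete ones. Two analysts could reach different primary counts from the same source.

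The section 9.7 figure raises a second, separate matter. A reader who sees an incidence rate expects ascertained events over a known period at risk. Here the events are passive reports and no period is given.

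**Working it through.** The plan states no count, rate or sample size to reproduce. The check is a reading of the rules, followed by simple algebra.

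**1. What can the section 9.2 rule mean?**
- *Every item from A1 to B5 must be present.* This cannot operate. A non-serious AE has no SAE onset (B1) or SAE causality (B2), and an AE is either solicited (B4) or unsolicited (B5), not both. Almost nothing would remain.
- *Every item relevant to the event must be present.* This can operate. An SAE then needs onset and causality, and one lacking either is not recorded.
- *An item missing for one outcome affects only that outcome.* This is the sensible rule, but the sentence does not say it. It withholds the whole event from analysis.

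The second reading is the workable one closest to the text, and the undefined exclusion in section 9.2.2 points the same way.

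**2. Effect on the counts under the second reading.** Let N be the SAEs reported, k those with missing onset or causality, M the non-serious AEs, and D the vaccines administered. N, k, M and D are not given. Considering this route alone:
- A1 = N − k instead of N.
- A2 = N + M − k instead of N + M.
- SAE figure under section 9.7 = (N − k)/D instead of N/D. The ratio of the two is 1 − k/N, because D does not change.
- Serious share in B3.1 = (N − k)/(N − k + M), which is below N/(N + M) whenever k and M are above zero.

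Illustration with assumed values of k/N:

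| k/N (assumed) | A1 as a fraction of SAEs reported |
|---|---|
| 5% | 1 − 0.05 = 0.95 |
| 10% | 1 − 0.10 = 0.90 |
| 20% | 1 − 0.20 = 0.80 |
| 30% | 1 − 0.30 = 0.70 |

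**3. How likely is a missing value?** An SAE known to have begun on a later day can be placed in the >30 min class without a clock time, so missing onset may be uncommon. B2 has the classes unclassifiable and indeterminate, which might absorb some SAEs without an assessment, but the plan does not say so. B1 has no residual class.

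**4. What period does the section 9.7 figure cover?** Sections 9.2 and 9.5 fix only calendar limits, from introduction of the vaccine to study approval. A dose given on the cut-off date has 0 days in which to yield a report; a dose given at introduction has the whole period. The length matters: with a constant background event rate and full reporting (both assumptions), background events per dose grow in proportion to the window. A 42-day window gives 42/28 = 1.5 times the events of a 28-day window, and a 365-day window gives 365/28 ≈ 13 times. A figure with a mixed, unstated window therefore cannot be set beside one with a known window.

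**The case against.** The strongest reply is that the section 9.2 sentence is loosely worded rather than harmful. Its literal sense cannot operate, so nobody would apply it that way, and k may be zero. This stands as far as size is concerned: no understatement has been demonstrated. It does not rescue the rule, because the nearest workable reading still removes SAEs and nothing exempts A1.

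A second reply is that the data management plan promised in section 9.6 may settle the handling of missing items. That is possible; it is not among the documents. If it does, a cross-reference would be enough for that part. Section 9.6 itself says only that data are obtained "as per the variables listed in section 9.3", which does not address missing values.

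A third reply is that section 9.7 states its numerator and denominator openly and that the calendar limits are given. Both are true, so the period is not unlimited. What remains is the label and the missing limitation.

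A reader might also infer that the 30-minute split, or the lack of a maximum onset interval, causes these problems. The documents do not support that. The possible loss from A1 comes from the exclusion rules in sections 9.2 and 9.2.2, and a maximum interval would not cure it. The rate problem comes from the definition in section 9.7, which covers all events, whereas onset is recorded for SAEs only. B1 does what it sets out to do, which is to separate immediate from later SAEs. No stated objective asks for finer timing, and the documents do not show that the source holds it.

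**Conclusion.** The point holds as a fault in the exclusion rules and, separately, in the label of the section 9.7 figure. If sections 9.2 and 9.2.2 are applied to the items relevant to an SAE, each SAE with missing onset or causality lowers A1 and A2 by one and lowers the SAE figure under section 9.7 by the fraction k/N. Through this route the error can only be downward. Its size cannot be derived from the documents and may be small. The conclusion rests on the second reading in the working and on the data management plan not already providing otherwise.

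It would go too far to say that the SAE count is known to be understated, or that the onset classes are wrong. The correction is worth making because A1 is a primary outcome and the remedy is inexpensive.

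**What to change.** 1. **Sections 9.2 and 9.2.2.** Restate the rule by outcome. Every SAE reported after a primary or booster dose stays in A1 and A2. Missing onset is shown as unknown/missing in B1, and missing causality likewise in B2. Define what incomplete means for the remaining items. Check that SAEs with missing onset or causality were not already dropped from the extract, and recover any that were.
2. **Sections 9.7 and 9.9.** Report events per vaccine administered as a reporting ratio, not an incidence rate. State in section 9.9 that the reports are passive, that no post-dose window is defined, and that follow-up varies with vaccination date up to the calendar cut-off.
3. **Optional, and not part of the error.** If the source already holds onset dates or intervals, the >30 min class could be split into intervals fixed before tabulation, keeping the 30-minute line.

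**Cost.** Items 1 and 2 are short text changes, but they amend the protocol, and section 10.4 requires prospective ethics approval of amendments. Some SAEs will appear as unknown. Planned data collection ended on 28 March 2023, 29 days before this version of 26 April 2023 (3 days left in March + 26 in April). Recovering dropped SAEs may therefore need a supplementary extract, which depends on the data owner (section 9.9). The planned report date of 19 June 2023 is 54 days after this version (4 + 31 + 19).
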